Study evaluation parameters and the schedules of assessment are presented in the Table 1. A window of +/- 3-days is allowed for all study assessments indicated on this trial except for which otherwise indicated. However, dosing windows for talimogene laherparepvec are Day 22 + 3 days for the initial dose and +/- 3 days for any subsequent cycles; dosing would be taken into account in the schedules of assessment.

Table 1. Study evaluation parameters and the schedules of assessment:

Evaluation	Pre-Tx	Day 1 (Week 1)	Day 22 (Week 4)	Day 36 (Week 6) & every 2 weeks during Tx Phase	Day 64 ± 1 week	At surgery or Bx	Post-surgery or Bx follow up ⁹	Follow up (every 12 weeks for 2 years ¹⁰)	At progression
History & Physical Exam ECOG PS Tumor Site Assessment	X ²	X	X	X			X	X	X
Pregnancy Test	X ²								
Talimogene laherparepvec Treatment		X	X	X					
Panitumumab Treatment			X	X					
Toxicity Assessment	X	X	X	X			X	X	
Photo of Tumor	X ⁴				X ⁴				X ⁴

Version Number: v10, March 23, 2023

Protocol Number: #091804

PI Name: [name]

Protocol Title: A Phase I Study of Talimogene laherparepvec and Panitumumab in Patients with Locally Advanced Squamous Cell Carcinoma of the Skin (SCCS)

RESERVED FOR IRB STAMP
DO NOT MODIFY THIS SPACE

RUTGERS | eIRB
APPROVED

IRB Form Version 12.18.2018

IRB ID:

Approval Date:

4/12/2023

Expiration Date:

9/21/2023

Surgical evaluation					X ⁴				
Tumor Biopsy or Resection	X ³					X			X ⁵
CBC with Differential	X ²	X	X	X				X	
Basic Metabolic Panel + Mg	X ²	X	X	X				X	
Hepatic Function Panel	X ²	X	X	X				X	
Radiographic Assessments ¹	X ¹				X ¹			X ¹	X ⁵
DNA Sequencing	X ⁶					X ⁶			X ⁶
mRNA Sequencing	X ⁷					X ⁷			X ⁷
IHC and Flow Cytometry	X ⁸					X ⁸			X ⁸

1- Tumor assessments as indicated by investigator (e.g. PET/CT, CT C/A/P, MRI) as needed, no more than 1 month prior to treatment. First assessment to be followed by evaluation by surgery for complete surgical resection. Photos and scans to be completed at each restaging time point. Surgeon will assess optimal timing of procedure once therapy initiated. Following surgery, patients will have radiographic assessments every 12 weeks to monitor disease status. Patients who did not have surgery will have radiologic assessments every 12 weeks.

2- Baseline labs, blood tests, and EKG (electrocardiogram), need to be done within 14 days of treatment.

3- First biopsy within 30 days of initial treatment.

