If repeat local site imaging fails to confirm PD by irRC and the subject continues to be clinically stable, treatment may continue and follow the regular imaging schedule. When feasible, subjects should not be discontinued until PD is confirmed by the local site investigator radiology assessment. This allowance to continue treatment despite initial radiologic PD takes into account the observation that some subjects can have a transient tumor flare in the first few months after the start of immunotherapy, and then experience subsequent disease response. Subjects who are deemed clinically unstable are not required to have repeat tumor imaging for confirmation of PD.

1.3.3 Assessing Toxicity and Adverse Events:

All patients who receive one dose of protocol therapy will be evaluable for assessment of toxicity. Prior to

Version Number: v10, March 23, 2023

Protocol Number: #091804

PI Name: [name]

Protocol Title: A Phase I Study of Talimogene

Laherparepvec and Panitumumab in Patients with
Locally Advanced Squamous Cell Carcinoma of the
Skin (SCCS)

14

RESERVED FOR IRB STAMP
DO NOT MODIFY THIS SPACE

RUTGERS | eIRB
APPROVED

IRB Form Version 12.18.2018

IRB ID:

To 2018002628

Approval Date:

4/12/2023

Expiration Date:

9/21/2023

each cycle, the treating physician will fully assess the patient's condition with respect to possible treatment related toxicities. All adverse events, whether observed by the physician or reported by the patient, occurring during the active portion of therapy, or up to 30 days after the last dose of treatment will be graded by a numerical score according to the NCI's Common Terminology Criteria for Adverse Events (CTCAE), Version 4.0 (see <http://ctep.cancer.gov/reporting/ctc.html>) and recorded in the patient's medical record. For the purposes of reporting laboratory abnormalities, only Grade 3-4 adverse events will be recorded on the adverse event CRF pages. Grade 1-2 laboratory abnormalities will not be recorded on the adverse event CRF pages. Information entered on the adverse event CRF pages will include:

- 1) Specific type and duration of reaction (i.e., start and stop dates, resolution)
- 2) Severity/grade
- 3) Relationship to study drug (causality, attribution)
- 4) Management of the event, if treated with medication and other actions taken to alleviate the clinical event
- 5) Whether or not it was considered a SAE

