Dose modifications will follow the guidelines below. In general, therapy will continue with grade 1 or tolerable grade 2 toxicities. Intolerable grade 2, grade 3, or grade 4 toxicities will result in holding therapy as follows:

1.7.6.1 Dose modification guidelines for talimogene laherparepvec:

Reductions

Dose reductions with regards to changes in the concentrations of talimogene laherparepvec are not permitted. However, patients may require a reduction in the volume injected due to a disease response or due to local toxicity at the injection site. However, if in the course of administration of talimogene laherparepvec the subject cannot tolerate the full dose due to an injection-related adverse event such as pain, the total volume given should be recorded, and the reason for intolerance should be documented as an adverse event.

1.7.6.2. Talimogene Laherparepvec Dosage Adjustments, Delays, Rules for Withholding or Restarting, Permanent Discontinuation:

If talimogene laherparepvec treatment was delayed by > 2 weeks, that dose will be deemed to have been missed and the subject will proceed to the next scheduled treatment visit. Dose reductions of talimogene laherparepvec is not permitted, other than a reduction in the volume injected due to a disease response. CTCAE 4.0 criteria listed in Table 7 are used to determine toxicity grades.

If a subject experience any of the following treatment-related toxicities, talimogene laherparepvec administration should be delayed until the toxicity has resolved to at least CTCAE grade 1 or baseline (Table 7):

- grade 2 or greater immune-mediated adverse events, with the exception of vitiligo.
- grade 2 or greater allergic reactions.
- any other grade 3 or greater hematologic or non-hematologic toxicity.

Table 7. CTCAE 4.0 Criteria:

Symptom	Grade 1	Grade 2	Grade 3	Grade 4
---------	---------	---------	---------	---------

Version Number: v10, March 23, 2023

Protocol Number: #091804

PI Name: [name]

Protocol Title: A Phase I Study of Talimogene
Laherparepvec and Panitumumab in Patients with
Locally Advanced Squamous Cell Carcinoma of the
Skin (SCCS)

26

RESERVED FOR IRB STAMP
DO NOT MODIFY THIS SPACE

RUTGERS | eIRB
APPROVED

IRB Form Version 12.18.2018

IRB ID:

2018002628

Approval Date:

4/12/2023

Expiration Date:

9/21/2023

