In one study [44], dermatologic toxicities occurred in 90% of patients and were severe (grade 3 and higher) in 15% of patients receiving panitumumab. The clinical manifestations included, but were not limited to acneiform dermatitis, pruritus, erythema, rash, skin exfoliation, paronychia, dry skin, and fissures. Monitor patients who develop dermatologic or soft tissue toxicities while receiving panitumumab for the development of inflammatory or infectious sequelae. Withhold or discontinue panitumumab for dermatologic or soft tissue toxicity associated with severe or life-threatening inflammatory or infectious complications. Patients should be advised to avoid sun exposure while receiving panitumumab.

In previous reports, the Common Terminology Criteria for Adverse Events (CTCAE) 4.0 (Table 7) have been used for EGFR-associated rash.

4) Interstitial Lung Disease (ILD)

ILD may be acute in onset and has been observed in 1.3 % of patients, and some cases have been fatal. If patients experience worsening of respiratory symptoms such as dyspnea, cough and fever, panitumumab should be interrupted and the patient should be promptly investigated. If ILD is confirmed, panitumumab should be discontinued and the patient treated appropriately.

5) Electrolyte Abnormalities

Progressively decreasing serum magnesium levels leading to severe (grade 3-4) hypomagnesemia occurred in up to 7% [45] of patients across clinical trials. Monitor patients for hypomagnesemia and hypocalcemia prior to initiating treatment with panitumumab, periodically during treatment, and for up to 8 weeks after the completion of treatment. Other electrolyte disturbances, including hypokalemia, have also been observed. Replete magnesium and other electrolytes as appropriate.

6) Infusion Reactions

In one study [44], 4% of patients receiving panitumumab experienced infusion reactions, and 1% of patients experienced severe infusion reactions (grade 3-4). Infusion reactions, manifesting as fevers, chills, dyspnea, bronchospasm, and hypotension, can occur following panitumumab administration. Table 9 and 10 show the grading criteria for infusion reactions and dose modifications for infusion reactions, respectively. Fatal infusion reactions occurred in post-marketing experience.

Table 9. Grading Infusion Reactions:

	Grade 1	Grade 2	Grade 3	Grade 4

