of patients with a best ORR characterized as either a Complete Response (CR) or Partial Response (PR) relative to the total number of evaluable patients. Only patients with measurable disease at baseline will be included in the analysis of the objective response.

Durable response rate is defined as the percent of patients with complete response or partial response maintained continuously for a minimum of 6 months. Response duration is defined as the time from initial response until documented progression.

For subjects converted to resectable and surgical resection is performed (complete or partial), response endpoints will be censored at the time of surgery. However, these patients will still be followed for PFS and OS.

6.1.5 Toxicity Monitoring and Adverse Event Reporting:

All patients who receive one dose of protocol therapy will be evaluable for assessment of toxicity. Prior to each cycle, the treating physician will fully assess the patient's condition with respect to possible treatment related toxicities. All adverse events, whether observed by the physician or reported by the patient, occurring during the active portion of therapy, or up to 30 days after the last dose of treatment will be graded by a numerical score according to the NCI's Common Terminology Criteria for Adverse Events (CTCAE), Version 4.0 (see <http://ctep.cancer.gov/reporting/ctc.html>) and recorded in the patient's medical record. For the purposes of reporting laboratory abnormalities, only Grade 3-4 adverse events will be recorded on the adverse event CRF pages. Grade 1-2 laboratory abnormalities will not be recorded on the adverse event CRF pages. Information entered on the adverse event CRF pages will include:

- 6) Specific type and duration of reaction (i.e., start and stop dates, resolution)
- 7) Severity/grade
- 8) Relationship to study drug (causality, attribution)
- 9) Management of the event, if treated with medication and other actions taken to alleviate the clinical event
- 10) Whether or not it was considered a SAE

A preexisting condition is one that is present at the start of the study. A preexisting condition will be recorded as an adverse event if the frequency, intensity, or the character of the condition worsens during the study period.

6.1.5.1. Adverse Event Reporting Requirements:

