6.2 Data Security

Wherever feasible, Electronic Data Capture (EDC) will be utilized for collecting subject data. All study personnel are required to have a computer and internet connection available for entry of clinical data. All entries in the eCRF will be made under the e-signature of the person performing the action. This electronic signature consists of an individual and confidential username and password combination. Only PI/Investigator authorized users will have access to the eCRF as appropriate to their study

Version Number: v10, March 23, 2023

Protocol Number: #091804

PI Name: [name]

Protocol Title: A Phase I Study of Talimogene

Laherparepvec and Panitumumab in Patients with
Locally Advanced Squamous Cell Carcinoma of the
Skin (SCCS)

RESERVED FOR IRB STAMP
DO NOT MODIFY THIS SPACE

RUTGERS | eIRB
APPROVED

IRB Form Version 12.18.2018

IRB ID:

Approval Date:

Expiration Date:

2018002628

4/12/2023

9/21/2023

responsibilities. Users must have successfully undergone software application training prior to entering data into the eCRF.

For non EDC elements, the PI will ensure that appropriate data entry methods are used (e.g. double data entry) and suitable queries are raised to resolve any missing or inconsistent data.

6.2.1 Case Report Forms:

A subset of the National Cancer Institute (NCI) CRFs, in electronic format, will be utilized. Completion of the electronic CRFs (eCRFs) will be done in accordance with the instructions in a study specific data capture plan. All eCRFs will be completed by clinical research coordinators of the OHRS. The eCRFs will be maintained in a confidential format in a secure database.

6.2.2 Data Submission Timeline and Forms:

Completion of eCRFs will occur in accordance with NCI guidelines. Baseline (pre-study) eCRFs (e.g., enrollment, medical history, concomitant medications, disease assessment, etc.) will be completed no later than 14 days after the start of treatment. Treatment eCRFs (e.g., drug administration, adverse events, chemistries, etc.) will be completed no later than 14 days following each cycle of treatment. Off-treatment information (e.g., follow-up, best response, etc.) will be completed no later than 14 days after the end of protocol treatment.

6.2.3 Research Charts:

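### Grade 1-2 laboratory abnormalities are kept off the AE CRF with no exception for those that change treatment, and no graded summary of the chemistry data is planned

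*Combined protocol and SAP*

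**What the plan says.** **Recording.** Sections 1.3.3 and 6.1.5 carry the same rule: "For the purposes of reporting laboratory abnormalities, only Grade 3-4 adverse events will be recorded on the adverse event CRF pages", followed by "Grade 1-2 laboratory abnormalities will not be recorded on the adverse event CRF pages". All adverse events are still to be "graded by a numerical score according to the NCI's Common Terminology Criteria for Adverse Events (CTCAE), Version 4.0" and entered in the medical record, so the exclusion concerns the AE CRF only. That CRF is where type and duration, grade, relationship to study drug, management and seriousness are captured.

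**Laboratory data.** Table 1 schedules "Basic Metabolic Panel + Mg" and a hepatic panel before treatment, on days 1, 22 and 36, every 2 weeks during treatment, and in follow-up. Section 6.2.2 says: "Treatment eCRFs (e.g., drug administration, adverse events, chemistries, etc.) will be completed no later than 14 days following each cycle of treatment".

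**Known toxicity.** Section 1.7.6.3, item 5, says: "Progressively decreasing serum magnesium levels leading to severe (grade 3-4) hypomagnesemia occurred in up to 7% [45] of patients across clinical trials". No rate is given for grade 1-2 or for all grades.

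**Action at grade 2.** Section 1.7.6.2 delays talimogene laherparepvec for treatment-related "grade 2 or greater immune-mediated adverse events, with the exception of vitiligo". Section 1.7.6 also holds therapy for grade 2 toxicity that is intolerable.

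**Analysis and reporting.** Section 6.1.1 promises descriptive statistics for the outcome measures, and the safety outcome listed in 1.6.2 is AEs. No laboratory summary is named. Section 6.2.4 says that publications and annual reports are written from the eCRF data.

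**The concern.** Leaving incidental low-grade laboratory values off the AE CRF is a common economy. The difficulty here is that the rule has no exception, while other parts of the same protocol act on events below grade 3. A laboratory event can therefore be important enough to delay a drug or an operation and still be one that the site is told not to enter.

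Safety of the combination is primary objective 1. If the safety report is built from the AE CRF, as 6.1.1, 1.6.2 and 6.2.4 together imply, two things follow. Low-grade magnesium and other electrolyte falls, which belong to a known panitumumab toxicity, would be undercounted. Some treatment or surgery delays could also appear with no adverse event behind them, so that their cause, management and duration could not be tabulated.

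**Working it through.** The plan states no figure on this point to reproduce. The check traces where a grade 1-2 laboratory event would be recorded and then bounds the size for hypomagnesemia.

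**Step 1. Where the event goes.**

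| Route | Section | Does it supply a safety summary? |
|---|---|---|
| AE CRF | 1.3.3, 6.1.5 | No; excluded without exception |
| Medical record | 1.3.3, 6.1.5 | Graded there, but reports are written from eCRFs (6.2.4) |
| Chemistry eCRF | 1.9.1, 6.2.2 | Values should be held; no grading or table is planned (6.1.1) |
| Drug-administration eCRF | 1.9.1, 6.2.2 | Doses should be held; not attribution or management of an event |
| Expedited reports | 6.1.5.1 | Only if the event is serious or unexpected |

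The underlying values and doses are recoverable. The AE record, and any planned output that grades the values, are missing.

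**Step 2. Where the plan uses events below grade 3.**
- Section 1.7.6.2 delays talimogene laherparepvec from grade 2 for immune-mediated events.
- One talimogene DLT criterion in 1.7.9.1, intolerable toxicity that ends the drug, has no grade limit.
- The stopping rule in 6.1.2 counts hospitalization, or delayed or cancelled surgery, from treatment-related toxicity with no grade limit. The 30% rule in 1.5 and 6.1.3.2 counts only grade 3 or higher.
- Table 13 in 6.1.5.3 requires a listing and tabulation of all adverse events, serious or not. An AE CRF completed under the rule cannot supply that in full.

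**Step 3. Size for hypomagnesemia.** Inputs are n = 30 (1.3, 1.5) and a grade 3-4 rate of 7%, the upper figure in 1.7.6.3.

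Grade 3-4 cases, which the rule does record:
- Expected: 30 × 0.07 = 2.1
- P(none) = 0.93^30 = 0.113, so P(at least one) = 0.887
- P(one or none) = 0.113 + 30 × 0.07 × 0.93^29 = 0.369

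Patients whose worst grade is 1-2, which the rule excludes, number 30 × (q − 0.07), where q is the all-grade rate. The documents do not give q, so a range is assumed:

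| Assumed q | Grade 1-2 only, of 30 | Share of all cases, (q − 0.07)/q |
|---|---|---|
| 10% | 0.9 | 30% |
| 14% | 2.1 | 50% |
| 20% | 3.9 | 65% |
| 30% | 6.9 | 77% |
| 40% | 9.9 | 82.5% |

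The share passes one half only when q exceeds 2 × 0.07 = 14%.

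**The case against.** The strongest reply is that the rule closes one destination and leaves the others open. Panels are drawn every 2 weeks on treatment, chemistries and drug administration have their own eCRF pages, and serious or unexpected events are reported whatever their grade. The general DLT definition in 1.7.9 and the 30% rule in 1.5 start at grade 3, so the main safety decisions are largely untouched. On this view the gap is one unspecified table.

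Much of this stands, and it rules out several stronger readings that a reader might infer.

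- *That low-grade laboratory events never reach the safety analysis.* The values should be in the database through the chemistry eCRF. What is absent is a plan to grade and report them.
- *That most panitumumab hypomagnesemia would be lost.* This needs an all-grade rate above 14%. That is plausible, but no figure in the documents shows it.
- *That immune-mediated diagnoses are barred.* The rule covers laboratory abnormalities. Glomerulonephritis, vasculitis and pneumonitis, which the protocol names, are clinical diagnoses and can be entered. The gap concerns an event whose only sign is a laboratory value, such as a grade 2 creatinine or transaminase rise. Section 1.7.6.4 allows for involvement of any organ system, so such a case is possible, but nothing shows how often it would occur.
- *That the 2.1 expected cases and their probabilities measure the loss.* They describe grade 3-4 events, which are recorded. They show only that the AE table may contain few cases: one or none with probability 0.369 if the rate is 7%.

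The reply does not answer two things. Chemistry and dosing pages do not carry attribution, management or event duration. Expedited reporting does not help with low-grade hypomagnesemia, which 1.7.6.3 lists as a panitumumab toxicity and which would ordinarily be neither serious nor unexpected.

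**Conclusion.** The point holds in a limited form. Followed as written, the plan gives AE summaries that understate low-grade electrolyte abnormalities. It also allows a grade 2 laboratory event that delays talimogene laherparepvec or surgery to have no AE record. The rule is out of step with Table 13 and with the stopping rule in 6.1.2.

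The size cannot be fixed from the documents. For hypomagnesemia, 0.9 to 9.9 of 30 patients is the span for assumed all-grade rates of 10% to 40%, taking the grade 3-4 rate at its stated upper value of 7% and enrollment at the full 30. The conclusion also assumes that the safety tables are drawn from the AE CRF, which the plan implies but does not state outright. The two-stage response design is not affected. This should be corrected because it bears on a primary objective and the remedy is cheap.

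**What to change.** **Sections 1.3.3 and 6.1.5.** Keep the exclusion for incidental grade 1-2 values and add: *A grade 1-2 laboratory abnormality is nevertheless entered on the AE CRF, at its grade, if it is treated; leads to delay, reduction or discontinuation of either study drug; delays or cancels surgery; or is part of an immune-mediated event.*

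**Section 6.1.1.** Add: *For magnesium, calcium, potassium, creatinine, ALT/AST and bilirubin, CTCAE v4.0 grade is derived from the chemistry eCRF at each visit, and worst on-treatment grade is tabulated by baseline grade.* This table is needed as well as the exception, because an untreated low-grade fall that changes nothing would still be off the AE CRF. The on-treatment window should be stated: AE collection ends 30 days after the last dose, whereas 1.7.6.3 describes electrolyte monitoring for up to 8 weeks after treatment.

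**Reconcile.** Say how the Table 13 listing is produced under the recording rule. State the data source for the events counted in 6.1.2, and reconcile its absence of a grade limit with the grade 3 limit in 1.5 and 6.1.3.2.

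**Cost.** A few more AE entries and one shift table per analyte. The panels are already scheduled and chemistries already have an eCRF. The documents do not list panel contents, so it should be confirmed that all the named analytes are captured. No dose, clinical rule, sample size or error rate changes.

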1.4 Preliminary Data

1.4.1 Panitumumab in SCCS:

Anti-EGFR antibodies have been shown to have activity in squamous carcinomas of the skin [21]. In 2011, Maubec, et al., studied the anti-EGFR monoclonal antibody Cetuximab in 36 patients with unresectable SCCS and found a disease control rate of 69% [22]. Multiple published case and retrospective reports have documented tumor responses in patients with SCCS treated with Cetuximab, including one from our institution demonstrating an impressive complete response in an elderly patient with SCCS [23] (Figure 2). Panitumumab, a monoclonal antibody which inhibits the activity of the EGFR, is increasingly in use for systemic treatment of patients with advanced SCCS. In addition to EGFR inhibition, panitumumab induces antibody dependent, cell mediated cytotoxicity (ADCC) [24]. Panitumumab has shown activity in squamous carcinomas of the head and neck, and lung in combination with chemotherapy and/or radiation therapy [25-28], where its addition has been demonstrated to improve both median overall survival and progression free survival with an acceptable toxicity profile. Panitumumab has been studied prospectively as a single agent in a small cohort of patients with advanced SCCS [1]. While the sample size was small, panitumumab produced impressive response rates, including a best overall response rate of 31%, a complete response rate of 12.5%, as well as a median progression free survival and overall survival of 8 and 11 months, respectively [1]. Because of the impressive responses seen in some patients such as the case reported by our institution, current NCCN guidelines for treatment of advanced SCCS disease [29] include EGFR inhibitors as an option. Nonetheless, rigorous randomized, prospective trials assessing the effectiveness of EGFR inhibitors in SCCS are lacking. Additionally, resistance may develop quickly, making studies examining combination therapies warranted [30].

Version Number: v10, March 23, 2023

Protocol Number: #091804

PI Name: [name]

Protocol Title: A Phase I Study of Talimogene
Laherparepvec and Panitumumab in Patients with
Locally Advanced Squamous Cell Carcinoma of the
Skin (SCCS)

15

RESERVED FOR IRB STAMP
DO NOT MODIFY THIS SPACE

RUTGERS | eIRB
APPROVED

IRB Form Version 12.18.2018

IRB ID: 1402018002628

Approval Date:

4/12/2023

Expiration Date:

9/21/2023

